- 4. To determine the longitudinal effect of ETI on nutrition, gastrointestinal symptoms, gut inflammation and pancreatic function in children and adults with CF over an additional period of 5 years.
- 5. To determine the longitudinal effect of treatment with ETI on CF liver disease in children and adults with CF over an additional period of 5 years.
- 6. To determine the longitudinal effect of treatment with ETI on antibiotic treatment of pulmonary disease in children and adults with CF over an additional period of 5 years.
- 7. To determine the longitudinal changes in mental health outcomes associated with the use of ETI in children and adults with CF over a period of 5 years.

BACKGROUND AND SIGNIFICANCE

Cystic Fibrosis

Cystic fibrosis (CF) is the most common progressive life threatening genetic disease in Caucasians(1). Approximately 80,000 people in the world and 1,200 people in Ireland have CF, almost half of whom are children (CFRI annual report 2016). CF is a multisystem disorder caused by a mutation in a gene that encodes cystic fibrosis transmembrane conductance (CFTR) protein. Lung disease is responsible for the majority of the morbidity and mortality in CF. Predicted survival for individuals with CF currently exceeds forty years, however the current mean age of death is still in the twenties(1). Medications that can modulate the natural history of CF and minimize, or even prevent, the development of life-threatening consequences of CF have been long sought after, particularly if these can be commenced in young children prior to the development of organ damage and irreversible disease.

CF Lung Disease

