The International Depression Epidemiological Study (TIDES) revealed rates of depression and anxiety 2-3 times higher among PWCF ages \geq 12 years than in the general community (95).Elevated depression and/or anxiety in pwCF are associated with poorer Health-Related Quality of Life, engagement in risky behaviors, more missed appointments, worse adherence to daily treatments, increased rates of pulmonary exacerbations, higher healthcare costs, and mortality (96-104). The findings of TIDES led to widely disseminated CFF/European CF Society (ECFS) consensus statements recommending standardized protocols for prevention, screening, and treatment of depression and anxiety in adolescents and adults with CF(105,106,107).

Their major impact notwithstanding, the utility of the TIDES data is limited by: 1) the cross-sectional study design; 2) collection more than a decade ago, in the pre-CFTR modulator era; 3) exclusion of children with CF under the age of 12 years (108) and mental health comorbidities beyond depression and anxiety (109); and 4) inclusion of very few physical health variables. A large, multicenter, longitudinal, prospective study of a cohort of children and adults with CF and is required to advance our fundamental understanding of CF mental health in children. Mental health outcomes were not initially included in the RECOVER parent study but will be in use in the ENHANCE study – a similar longitudinal study examining the natural history of CF in the new era of CFTR modulators, running in the same centres and others. In turn, this data will inform future research, clinical guidelines, and development and delivery of evidence-based mental health interventions.

Treatment Adherence

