We carried out spirometry-controlled CT scans at baseline, one year and two years after the introduction of LUM/IVA in 35 children aged 6-11, homozygous for the F508del mutation. Standardization of the scanner output, protocol and data transfer was managed through the LungAnalysis team. Images were scored using the Perth Rotterdam Annotated Grid Morphometric Analysis (PRAGMA) scoring system. Over the course of 2 years on LUM/IVA, while improvements were seen in the mean air trapping scores, bronchiectasis scores increased (Table 2). These data suggest that LUM/IVA can improve air trapping but does not prevent the progression of bronchiectasis in these young children with CF. The data were presented at NACFC 2021 and currently being submitted for publication. Ongoing work is examining the airway wall and artery dimensions in detail in these sans using specifically developed proprietary software in an automated fashion.

PRAGMA Score	E	Baseline		Year 1			
	Mean (95% CI) n=32		Mean (95% CI) n=32	Mean (p-value	
% Bronchiectasis	0.82	(0.48 - 1.16)	0.85	(0.51 - 1.19)	1.24	(0.89 - 1.60)	0.005
% Disease	2.78	(2.12 - 3.45)	2.46	(1.79 - 3.14)	2.25	(1.55 - 2.94)	0.138
% Trapped Air	0.13	(0.09 – 0.16)	0.10	(0.07 – 0.14)	0.07	(0.03 – 0.11)	0.016
% Mucous plugging	0.57	(0.31 – 0.83)	0.28	(0.01 - 0.54)	0.33	(0.04 - 0.62)	0.221

Table 2. Change from baseline in PRAGMA CT scores in 35 children homozygous for the F508del mutation, aged 6-11 on treatment with Lumacaftor/Ivacaftor.

PRELIMINARY data from RECOVER Parent Study

Despite unexpectedly accelerated approval of ETI in Europe in 2020 and a global pandemic, we have reasonable levels of recruitment to date (85% target) and retention of subjects in the first phase (12+) of RECOVER. One-year outcomes were presented at ECFS 2022 (Table 3 below) and Phase 2 of RECOVER (6-11) is continuing to recruit subjects. Figure 4 below shows significant differences in baseline (pretreatment) values for FEV1 and LCI in the 12+ and 6-11 groups, underlining the 'normalization' of LCI in younger children

P.I. [name]

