The design of RECOVER is specifically aimed at maximizing the research benefit (and ultimately the benefit to people with CF) from this cohort of children, adolescents and adults with CF. Our aim with this study is collect as comprehensive as possible an array of biological samples and clinical data from this cohort, and to follow them longitudinally. After the end of RECOVER, we envisage an ongoing surveillance study involving this group, in collaboration with our registry partners so that we can continue to learn about the longer-term impacts of these treatments. In addition, our sample storage plan associated with RECOVER will allow us to work with collaborators and collect, aliquot and store biological samples that will magnify the benefit of the study in light of the fact that these samples will be linked to a well phenotyped cohort with a wide array of useful clinical outcome measures.

EXPERIMENTAL DESIGN AND METHODS

Study Design

RECOVER is a multi-centre, cohort study which takes part in seven paediatric and adult sites across Ireland and the UK over a two-year period (parent study) and a further five years follow up (extension study) in conjunction with the CF Registry of Ireland (CFRI) and the UK CF registry. On the basis that drug will become available first for people aged 12 and over, the first phase, RECOVER12+ will recruit children 12 years and older and adults. This will be followed by the second phase, RECOVER6, recruiting children aged 6-11 years who will likely be starting on drug approximately a year after the older cohort. Data collection for each of these phases will occur over a two year period (Parent Study), and will overlap by 1-2 years. Subsequent to the twoyear period, participants will enter an extension study for a period of five years, with a scaled back programme of assessments occurring annually or biennially. For subjects in both these cohorts, the decision to implement Kaftrio treatment is made completely independently of the decision to enter the study. The investigators will

follow the requirements of the local approved Kaftrio SmPC for the patient management as detailed in the 'special warnings and precautions for use' (e.g. management of hepatic impairment, rash, ophthalmological monitoring, between others), and for the management of interaction with other medicinal products and other forms of interactions.

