In exceptional circumstances where baseline clinical data has been collected prior to the start of treatment either through clinical care or ethically approved research projects (including a cohort of subjects initially recruited to this study on the understanding that it was a non-regulated observational study) subjects already receiving ETI may be recruited to this study and undergo on-treatment visits. Any additional patient data can only be added with written informed consent from the patients/parents concerned.

P.I. [name]

All subjects must have a signed informed consent form and/or signed assent form when appropriate, as determined by the subjects age and individual site and country standards.

Male and female participants of childbearing potential must agree to adhere to contraception requirements as detailed in the local ETI SmPC and in line with the standard of care.

Exclusion criteria

Patients not willing to comply with study procedures or assessments.

Individuals on clinical trials of investigational CFTR modulators.

Clinical instability at baseline assessments. Subjects undergoing an active exacerbation and at the beginning of their treatment should be excluded from the study as this is likely to skew the data.

Any contraindication to ETI treatment as per the local approved SmPC.

Severe hepatic impairment.

Pregnant and breastfeeding women.

Inclusion and Exclusion Criteria for Extension Study

Inclusion criteria

Children and adults with CF who have completed two years participation on the parent study, and are willing to provide informed consent for continued data and bio-sample collection for a period of five years.

Exclusion criteria

Participants not willing to comply with study procedures or assessments.

Individuals on clinical trials of investigational CFTR modulators.

Drug Interruption or Discontinuation of ETI

If a patient experiences a drug interruption, discontinues ETI and/or is prescribed TEZ/IVA, LUM/IVA or IVA, they can continue trial participation.

Advanced Testing v Standard Testing for the Parent Study

As outlined in Table 5, we will have a standard and advanced testing group for the parent study. In addition to all elements of the standard testing group, the advanced testing group will undergo:

- Ultra-low dose spirometry-controlled CT scanning
- Sputum collection
- Nasal lavage collection

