Sweat tests will be carried out on all individuals prior to initiation of treatment and then at 6 months after treatment, at one year and at two years for the parent study, and annually in the extension study. Sweat will be collected using the Macroduct sweat collection system as per manufacturer's instructions using pilocarpine iontophoresis to induce sweating. Sweat tests will be performed on both arms. Sweat will be stored in 0.2ml

P.I. [name]

PCR tubes and immediately transferred to the laboratory and frozen at -80°C. Sweat chloride will be analyzed in all stored sweat samples in batches by the Chloro-check Chloridometer (EliTech Group Inc.) at all sites.

Nutritional Indices

Height and weight will be measured at three monthly intervals throughout the duration of the parent study at each out-patient visit, and annually during the extension study. Height, weight and BMI z-scores will be calculated from these measurements.

Patient Reported Outcomes – Respiratory Symptoms

CFQ-R (including the CFQ-R treatment burden subscale) will be administered to study participants every six months during the parent study and annually during the extension study. Scores in all domains of CFQR will be compared between baseline and follow up visits.

Investigational Medicinal Product (IMP)

The IMP for this trial is ETI (EU/1/20/1468/001). This IMP is licenced for use in the United Kingdom and will be administered to study subjects in line with the prescription and in line with the SmPC. To be enrolled in the Parent Study, all patients were prescribed ETI. The decision to implement treatment with IMP is made completely independently of the decision to enter subjects into the study. If a patient experiences a drug interruption, discontinues ETI and/or is prescribed TEZ/IVA (EMEA/H/C/004682), LUM/IVA (EMEA/H/C/003954) or IVA (EMEA/H/C/002494) after enrolment, they can continue trial participation. IMP will be dispensed in accordance with usual clinical practice (i.e. by hospital pharmacy/community pharmacy) and therefore no additional labelling, QP batch release or drug accountability is required.

Recording and reporting of adverse events and reactions

Definitions

Torm	Definition					
Term						
Adverse Event (AE)	Any untoward medical occurrence in a patient or clinical trial					
	subject administered a medicinal product and which does not					
	necessarily have a causal relationship with this treatment.					

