Eligibility Assessment	Х	Х															
Sweat Chloride		Х				Х		Х				Х	Х	х	Х	х	Х
LCI	Х	Х				Х		Х		Х		Х	Х	Х	Х	Х	Х
Spirometry-controlled CT (A*)		Х						Х				Х		X1		X1	
Height/Weight/BMI*	Х	Х			Х	Х	Х	Х	Х	Х	Х	Х	Х	Х	Х	Х	Х
FEV1*	Х	Х			х	Х	Х	х	Х	Х	Х	Х	Х	х	х	Х	Х
Airway Sampling (Micro)*	Х	Х			Х	Х	Х	Х	Х	Х	Х	Х	Х	Х	Х	Х	Х
Nasal Lavage (A*)		Х				Х		Х				Х	Х	х	х	Х	Х
FeNO	Х	Х				Х		Х									
Liver Function Testing*		Х			Х	Х	Х	Х				Х	Х	х	Х	Х	Х
Liver Ultrasound		Х						Х				Х	Х	Х	Х	Х	Х
Sputum Collection (A*)		Х				Х		Х		Х		Х	Х	х	Х	Х	Х
Liver Examination		Х						Х				Х					
Stool Collection		Х	Х			Х						Х	Х	х	Х	Х	Х
Blood Collection		Х						Х				Х	Х	Х	Х	Х	Х
Breath Sample Collection		Х			Х	Х	Х	Х									
Abdominal Symptom Score	Х	Х	Х	Х		Х		Х				Х	Х	х	Х	Х	Х
CFQ-R		Х				Х		Х				Х	Х	Х	Х	Х	Х
Pharmacy Records MPR								Х				Х					
Adherence Questionnaire	Х	Х			Х	Х	Х	Х	Х	Х	Х	Х					
MEMs Caps Reading (M)								Х				Х					
Antibiotic Use		Х						Х				Х					
Adverse Event Check			Х	Х	Х	Х	Х	Х	Х	Х	Х	Х	Х	Х	Х	Х	Х
Mental Health Questionnaire													Х	Х	Х	Х	Х

* Collected as normal clinical care,

A - Advanced arm testing in RECOVER parent study

¹ Only for patients who performed spirometry-controlled CT in parent study. Scan at years four and six at sites doing routine clinical CT. Scan at year six for sites not performing biennial CT

M - MEMs study only

Table 14. Schedule of assessments. Each visit has a study window. For the RECOVER parent study the baseline visit (0 month visit) will have an 8 week pre commencement on ETI start window. The 1, 2 and 3 month visits have +/- 2 week window. The 6, 9, 12, 15, 18, 21 and 24 month visits have +/- 1 month window. For the RECOVER extension study each annual visit will have a window of +/- 4 month.

Study Governance and Management Plan

RECOVER

[figure not shown]

Figure 6 RECOVER study management structure.

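### Extension Aim 7 seeks mental health change associated with ETI, but the questionnaires start about three years after ETI, with no pre-ETI or extension-entry value

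*Protocol*

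**What the plan says.** The protocol's list of extension aims gives Aim 7 as determining the "longitudinal changes in mental health outcomes associated with the use of ETI in children and adults with CF over a period of 5 years". The Mental Health part of the Background explains the history: "Mental health outcomes were not initially included in the RECOVER parent study".

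In the schedule of assessments (Table 14), the row "Mental Health Questionnaire" is marked in the five extension columns only, Years Three to Seven. All twelve parent-study columns, from month -3 to month 24, are blank.

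Eligibility for the extension is limited to "Children and adults with CF who have completed two years participation on the parent study". Study Design says that "participants will enter an extension study for a period of five years, with a scaled back programme of assessments occurring annually or biennially". The note to Table 14 adds: "For the RECOVER extension study each annual visit will have a window of +/- 4 month". The same note lets the month-0 visit fall up to 8 weeks before ETI is started.

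The section on Specific Aim 7 for the extension plans a linear mixed model for each outcome, with a random patient intercept. Its fixed effects are age at ETI initiation, genotype, sweat chloride, nutritional status, caregiver burden, number of treatments and year.

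**The concern.** A change associated with starting a drug needs either a measurement before the drug or a group that did not receive it. For mental health the protocol schedules neither. Aim and schedule are both fixed in the protocol, so a separate analysis plan could not supply the missing measurement.

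Two misreadings are possible. If mental health shifts in the first months or years on ETI, that shift is already inside the first questionnaire, and a flat Year Three to Year Seven trend could be reported as no ETI-associated change. Conversely, a drift caused by adolescence, the move to adult care or calendar events could be reported as associated with ETI.

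**Working it through.** **Inputs.** Year Three is taken as month 36 and Year Seven as month 84 (Table 8 lists years 3 to 7 after year 2). Extension entry is month 24, the end of the two-year parent study. The extension window is 4 months either side. The month-0 visit may precede ETI by up to 8 weeks, about 1.8 months.

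**Timing of the first questionnaire.**
- Counted from month 0: 36 - 4 = 32 to 36 + 4 = 40 months.
- Counted from ETI start, if month 0 came the full 8 weeks earlier: 32 - 1.8 = about 30 months at the lower end. Overall range: roughly 30 to 40 months.
- Counted from extension entry: 36 - 24 = 12 months (8 to 16 with the window).
- Questionnaires before ETI: 0. At month 24: 0.

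**Span.**
- Nominal: (84 - 36)/12 = 4.0 years.
- With windows: (48 - 8)/12 = 3.3 to (48 + 8)/12 = 4.7 years.
- With a month-24 questionnaire: (84 - 24)/12 = 5.0 years.

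**What the model can separate.** Within a participant, each further year of follow-up adds one year to age, to calendar time and to time since ETI start. Current age equals age at ETI initiation plus time since initiation. With age at initiation and year in the model, the slope on year therefore carries ageing, calendar time and duration of ETI together. No listed fixed effect is a pre-ETI value, a comparator group or current ETI exposure.

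**How early change can be.** Table 3 (parent study, aged 12 and over) gives means at baseline, 6 and 12 months. The share of the 12-month change already present at 6 months is:
- Sweat chloride (85.78, 44.92, 44.23): 40.86/41.55 = 98%.
- ppFEV1 (83.65, 91.73, 92.11): 8.08/8.46 = 96%.
- CFQ-R respiratory domain (83.32, 97.20, 95.49): the 6-month gain of 13.88 exceeds the 12-month gain of 12.17.

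These means rest on different numbers at each visit and are not mental health measures. They show only that, in this cohort, other responses were essentially complete long before month 36. Whether mental health behaves the same way is unknown.

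**Comparison with other extension measures.** In Table 14, LCI, FEV1, sweat chloride, liver function tests, stool, abdominal symptom score and CFQ-R are all marked at months 0 and 24. The mental health row has neither.

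**The case against.** The strongest reply is that Aim 7 never promises a before/after comparison. The other six extension aims speak of an effect of ETI; Aim 7 alone speaks of changes associated with its use. The model is described as examining patient characteristics over time, and the Background is open that mental health was not in the parent study. On that view the plan is on-treatment follow-up with patient-level correlates, and the schedule supports it. This largely stands. It makes the wording of the aim the main thing to correct, but it does not remove the problem, because the wording still ties the change to ETI use.

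Three stronger readings are tempting and are not supported:
- A reader might infer that every questionnaire is completed on long-term ETI, so that the data hold no ETI-related contrast at all. The sections on drug interruption and on the IMP let participants who stop ETI or move to another modulator stay in the study. Age at ETI initiation and sweat chloride are also ETI-related covariates. However, the model has no term for stopping or switching, such a contrast would be confounded by the reason for it, and neither covariate replaces a baseline.
- A reader might infer that follow-up falls a fifth short of the stated 5 years. Five annual assessments in a five-year extension is a fair meaning of that phrase.
- A reader might infer that CFQ-R fills the gap. The protocol already plans that "Scores in all domains of CFQR will be compared between baseline and follow up visits", but CFQ-R is not an Aim 7 instrument.

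A month-0 questionnaire for children not yet treated is also not a firm remedy. It would rest on the statement that "Phase 2 of RECOVER (6-11) is continuing to recruit subjects", which is dated, and whether any untreated child remains is unknown.

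**Conclusion.** The point holds as a mismatch between the aim and the data. With the first questionnaire at nominal month 36 (roughly 30 to 40 months after ETI start), no pre-ETI or month-24 value, and no comparator or exposure term, the study can describe mental health and its patient-level correlates during established ETI treatment. It cannot show change since before ETI, and it cannot separate a later trend on ETI from ageing and calendar time. The 4-year nominal span is secondary.

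This assumes that Year Three means the 36-month visit. If it meant any point in the third year, the first questionnaire could fall earlier, but the nominal span would stay at 4 years and there would still be no pre-ETI value. It also assumes no pre-ETI mental health data from elsewhere. The Background mentions ENHANCE as using such measures, but nothing in the protocol says that it supplies values for RECOVER participants.

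**What to change.** 1. Reword Aim 7 to change in mental health, and its patient-level correlates, during established ETI treatment. State that no before/after-ETI inference will be drawn from these scales. This works for every participant, whatever stage they have reached.
2. Mark the mental health questionnaires in Table 14 at the existing month-24 visit for participants who have not yet passed it. They would then have an extension-entry baseline and a nominal 5.0-year span, though still no pre-ETI value.

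The cost is protocol wording and one extra questionnaire set, with extension consent and the distress protocol in place by that visit. The main downside is selective missingness. Those already past month 24 cannot supply the entry value. They are probably mostly the 12+ cohort (137 of the 254 planned in Table 6), since Table 3 already reports 12-month data with N=90 for that group. Analyses that use the entry value should therefore be reported by cohort.
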